8.1.1 Rules for Handling Missing Data

Handling of missing data for the statistical analysis is described below:

For the primary efficacy analysis, a linear mixed model for repeated measures will be used to handle missing data. Under the Missing At Random (MAR) assumption, this model provides an unbiased estimate of the treatment effect that would have been observed if all subjects had continued on treatment for the full study duration. This approach addresses efficacy (or de jure) hypotheses, estimating the causal effects of the initially randomized drug if taken as directed (in contrast with effectiveness, or de facto, hypotheses, evaluating the effect of the drug as actually taken). The efficacy estimand is considered appropriate in the context of a phase II study aiming at characterizing dose-response.

The specific ways how to deal with missing data, in particular with partial or missing dates (e.g., of medication use), missing spirometry data and missing questionnaire data, is laid out in detail in the description of the variable derivation in the subsections under Section 7.2.

Other critical missing data, if any, will be discussed during the blind review of the data. Decisions will be fully documented in the Data Review Report.

8.2 Specific Methods for Efficacy Analyses

Analyses Based on Mixed Models

Primary efficacy endpoint

- Primary Model for Analysis

The change from baseline in pre-dose morning FEV₁ at week 8 will be analyzed using a linear mixed model for repeated measurements including treatment, visit, treatment by visit interaction, ICS dose before study (low/medium daily dose) and US regions as fixed effects, and the baseline value (average of the pre-dose FEV₁ measurements on Day 1) and baseline by visit interaction as covariates. An unstructured covariance matrix will be assumed; the generic code for the model is presented below.

```
proc mixed data = <xxx>;
class subject treatment visit usregion ICSdose;
model <response> = treatment visit treatment*visit usregion ICSdose fev1base fev1base*visit / DDFM=KR;
repeated visit / subject=subject type=UN;
lsmeans treatment*visit / cl OM AT MEANS;
lsmestimate treatment*visit 'Trt A vs Placebo week 8' 0 1 0 0 0 0 0 -1 0 0,
    'Trt B vs Placebo week 8' 0 0 0 1 0 0 0 -1 0 0,
    'Trt C vs Placebo week 8' 0 0 0 0 0 1 0 -1 0 0 / cl adjust=simulate (seed=12311980 acc=0.0001);
lsmestimate treatment*visit 'Trt B vs Trt A week 8' 0 -1 0 1 0 0 0 0 0 0 /cl;
lsmestimate treatment*visit 'Trt C vs Trt A week 8' 0 -1 0 0 0 1 0 0 0 0 /cl;
lsmestimate treatment*visit 'Trt C vs Trt B week 8' 0 0 0 -1 0 1 0 0 0 0 /cl;
lsmestimate treatment*visit 'Trt E vs Placebo week 8' 0 0 0 0 0 0 0 -1 0 1 /cl;
```

run;

where:

- *treatment* is the randomized treatment variable, codified and sorted as follow:
 1. Treatment A (BDP 100µg)
 2. Treatment B (BDP 400µg)
 3. Treatment C (BDP 800µg)
 4. Placebo
 5. Treatment E (QVAR 320 µg)
- *visit* is the visit variable (Visit 3 [week 4] and Visit 4 [week 8])
- *treatment*visit* is the treatment by visit interaction
- *usregion* is the region in the United States from which the subject entered the study (Midwest, Northeast, South and West Regions).
- *ICSdose* is the ICS dose before the study (low/medium daily dose)
- *fev1base* is the baseline FEV₁ result
- *fev1base*visit* is the baseline FEV₁ result by visit interaction.

The adjusted means in each treatment group, the adjusted mean difference between treatments and their 95% Confidence Intervals (CIs) will be estimated by the model. The CIs and the p-values of the comparisons between each dose of CHF 718 pMDI and placebo at Week 8 will be adjusted for multiplicity. For the primary endpoint, the adjustment will be based on the parametric simulation method by Edwards and Berry (adjust=simulate in the MODEL statement). The random number seed will be set equal to 12311980, and 0.0001 will be used for the target accuracy radius gamma (i.e. ACC=0.0001). At each dose level, the superiority of CHF 718 pMDI will be demonstrated by a **statistically significant** difference (adjusted p-value < 0.05) favoring CHF 718 pMDI.

The model will include also pairwise comparisons of treatment A through treatment C, comparing each dose with a lower dose, and treatment E versus Placebo. The CIs and the p-values of these comparisons at Week 8 will not be adjusted for multiplicity.

Kenward Roger's method will be used to approximate denominator degrees of freedom (/DDFM=KR in the MODEL statement); OM and AT MEANS in LSMEANS statement will be used to account for unbalanced population (see details in 8.1).

Sensitivity analysis:

Primary analysis will be repeated for sensitivity analysis considering the ICS dose as reported in the IVRS system at randomization.

Another sensitivity analysis, exactly as the primary analysis, will be repeated incorporating only the spirometry with Grade="Acceptable".

Secondary efficacy endpoints

For the secondary efficacy analyses (pre-dose morning FEV₁ at Week 4, pre-dose morning FVC at Week 4 and Week 8, ACQ-7 score at Week 4 and Week 8, average use of rescue medication, percentage of rescue medication-free days, daily asthma symptoms scores, percentage of asthma symptoms-free days, percentage of asthma control days, morning and evening pre-dose PEF) the same model as above defined for the primary efficacy variable will be used with no multiplicity adjustment.

The adjusted means in each treatment group, the adjusted mean difference between treatments and their 95% Confidence Intervals (CIs) will be estimated by the model. The CIs and the p-values of the comparisons between treatments at Week 4 or Week 8 will not be adjusted for multiplicity.

For analysis of use of rescue medication, rescue-medication free days, daily asthma symptoms scores, asthma symptoms-free days, asthma control days, morning and evening pre-dose PEF the inter-visit period will be considered instead of visit in the model. Comparison between treatments over the entire treatment period will also be derived from this model. The generic code for the model is presented below.

```
proc mixed data = <xxx>;
  class subject treatment inter_visit usregion ICSdose;
  model <response> = treatment inter_visit treatment*inter_visit usregion ICSdose base base*inter_visit /
    DDFM=KR;
  repeated inter_visit / subject=subject type=UN;
  lsmeans treatment treatment*inter_visit / cl OM AT MEANS;
  lsestimate treatment "Trt A vs Placebo entire tmt period" 1 0 0 -1 0 /cl;
  lsestimate treatment "Trt B vs Placebo entire tmt period" 0 1 0 -1 0 /cl;
  lsestimate treatment "Trt C vs Placebo entire tmt period" 0 0 1 -1 0 /cl;
  lsestimate treatment "Trt B vs Trt A entire tmt period" -1 1 0 0 0 /cl;
  lsestimate treatment "Trt C vs Trt A entire tmt period" -1 0 1 0 0 /cl;
  lsestimate treatment "Trt C vs Trt B entire tmt period" 0 -1 1 0 0 /cl;
  lsestimate treatment "Trt E vs Placebo entire tmt period" 0 0 0 -1 1 /cl;
  lsestimate treatment*inter_visit 'Trt A vs Placebo period 1' 1 0 0 0 0 0 -1 0 0 0 /cl;
  lsestimate treatment*inter_visit 'Trt B vs Placebo period 1' 0 0 1 0 0 0 -1 0 0 0 /cl;
  lsestimate treatment*inter_visit 'Trt C vs Placebo period 1' 0 0 0 0 1 0 -1 0 0 0 /cl;
  lsestimate treatment*inter_visit 'Trt B vs Trt A period 1' -1 0 1 0 0 0 0 0 0 0 /cl;
  lsestimate treatment*inter_visit 'Trt C vs Trt A period 1' -1 0 0 0 1 0 0 0 0 0 /cl;
  lsestimate treatment*inter_visit 'Trt C vs Trt B period 1' 0 0 -1 0 1 0 0 0 0 0 /cl;
  lsestimate treatment*inter_visit 'Trt E vs Placebo period 1' 0 0 0 0 0 0 -1 0 1 0 /cl;
  lsestimate treatment*inter_visit "Trt A vs Placebo period 2" 0 1 0 0 0 0 0 -1 0 0 /cl;
  ...
  lsestimate treatment*inter_visit "Trt E vs Placebo period 2" 0 0 0 0 0 0 0 -1 0 1 /cl;
run;
```

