12. STATISTICAL METHODS

12.1 Sample Size

The sample size has been calculated to evaluate the superiority of CHF 718 pMDI at different doses over placebo in terms of change from baseline in pre-dose morning FEV₁ at Week 8.

A total of 495 evaluable subjects (99 per group) will provide 80% power to detect a mean difference of 200mL between each dose of CHF 718 pMDI and placebo at a two-sided significance level of 0.0167, assuming a standard deviation of 430mL.

Since three dose levels will be tested, the Edwards and Berry method will be used to control the family-wise Type I error rate at the 0.05 (two-sided) level. In the sample size calculation, the Bonferroni adjustment of the significance level has been taken into account ($0.0167 = 0.05/3$). This will ensure the required power for each test, since the Edwards and Berry method is uniformly more powerful than the Bonferroni procedure.

Considering a non-evaluable rate of 15%, a total of approximately 585 subjects (117 per group) will be randomized.

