3.5 Sample Size Calculation

The sample size has been calculated to evaluate the superiority of CHF 718 pMDI at different doses over placebo in terms of change from baseline in pre-dose morning FEV₁ at Week 8.

A total of 495 evaluable subjects (99 per group) will provide 80% power to detect a mean difference of 200mL between each dose of CHF 718 pMDI and placebo at a two-sided significance level of 0.0167, assuming a standard deviation of 430mL.

Since three dose levels will be tested, the Edwards and Berry method will be used to control the family-wise Type I error rate at the 0.05 (two-sided) level. In the sample size calculation, the Bonferroni adjustment of the significance level has been taken into account ($0.0167 = 0.05/3$). This will ensure the required power for each test, since the Edwards and Berry method is uniformly more powerful than the Bonferroni procedure.

Considering a non-evaluable rate of 15%, a total of approximately 585 subjects (117 per group) will be randomized.

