8.2.1.4 Multiple Comparisons/Multiplicity

Adjustment for multiplicity is applicable only to the primary efficacy analysis. The CIs and the p-values of the comparisons between each dose of CHF 718 pMDI and placebo for the primary efficacy endpoint at Week 8 will be adjusted for multiplicity. The adjustment will be based on the parametric simulation method by Edwards and Berry. At each dose level, the superiority of CHF 718 pMDI will be demonstrated by a **statistically significant** difference (adjusted p-value < 0.05) favoring CHF 718p MDI.

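### The three primary dose-placebo tests use a valid single-step adjustment; a step-down form of the same method would add power within the same 0.05 family-wise bound

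*SAP*

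**What the plan says.** SAP 8.2 places the three Week 8 contrasts (A, B and C against placebo) in one LSMESTIMATE statement with the options "cl adjust=simulate (seed=12311980 acc=0.0001". SAP 8.2.1.4 says in words: "The adjustment will be based on the parametric simulation method by Edwards and Berry". SAP 10.6.1 and protocol 12.3.4 say the same. None of these sections mentions step-down testing, closed testing or an ordered hierarchy, so all three tests face one common critical value.

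The same sections declare superiority separately at each dose when the adjusted p-value is below 0.05. They also ask for the confidence intervals to be multiplicity-adjusted.

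On the purpose of the method, SAP 3.5 states that "the Edwards and Berry method will be used to control the family-wise Type I error rate at the 0.05 (two-sided) level". The sample size rests on Bonferroni: "A total of 495 evaluable subjects (99 per group) will provide 80% power", for 200 mL per dose, "at a two-sided significance level of 0.0167, assuming a standard deviation of 430mL". Protocol 12.1 explains why that is sufficient: "the Edwards and Berry method is uniformly more powerful than the Bonferroni procedure".

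**The concern.** Once one dose has been shown superior to placebo, only two hypotheses can still be falsely rejected; after a second, only one. A single-step procedure keeps the three-test critical value for all of them. A step-down procedure relaxes it as hypotheses are rejected and, by the closure principle, still controls the family-wise error strongly at 0.05.

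Because the SAP takes its decision from the p-value, nothing in the decision rule needs the stricter value for the second and third tests. What is at stake is power at the doses with smaller effects, and power to show all three. Protocol section 1 gives characterising the dose-response as the aim of the study, so the lower doses matter.

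**Working it through.** **Inputs from the documents (SAP 3.4 and 3.5).** 99 evaluable per arm; SD 430 mL; 200 mL difference from placebo at each dose; family-wise alpha 0.05 two-sided; equal allocation to five arms. Equal allocation with a shared placebo arm gives correlation 0.5 between the dose-placebo statistics.

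**Assumed.** 490 degrees of freedom (5 × 99 − 5). The documents give no value, and the Kenward-Roger figure from the mixed model will differ somewhat.

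**1. The plan's own figure.** SE = 430 × √(2/99) = 61.1 mL. Noncentrality = 200/61.1 = 3.27. The two-sided 0.0167 critical value on 196 df is 2.414. Noncentral-t power is 0.799 at n = 98 and 0.804 at n = 99, so 99 per arm reproduces. Then 99/0.85 = 116.5, rounded up to 117, and 5 × 117 = 585.

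**2. Critical values.** The two-sided many-to-one critical value c_k for k remaining doses solves P(max |T_j| ≤ c_k, j = 1..k) = 0.95 with correlation 0.5 and 490 df. The Edwards-Berry simulation approximates this limit.

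| Tests remaining | c_k | Nominal p | Observed difference needed (c_k × 61.1 mL) |
|---|---|---|---|
| 3 | 2.356 | 0.0189 | 144 mL |
| 2 | 2.219 | 0.0270 | 136 mL |
| 1 | 1.965 | 0.0500 | 120 mL |

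Single-step uses 2.356 for all three tests. Step-down orders |T| from largest to smallest, compares with 2.356, 2.219 and 1.965 in turn, and stops at the first failure.

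**3. Power, planning case (200 mL at every dose), 1,000,000 simulated trials.**

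| Procedure | Per dose | All three | At least one |
|---|---|---|---|
| Bonferroni | 80.8% | 62.4% | 95.3% |
| Single-step (planned) | 82.0% | 64.3% | 95.8% |
| Step-down | 87.6% | 78.0% | 95.8% |

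The gains over the planned method are 5.6 points per dose and 13.7 points for all three. With 117 per arm, the per-dose figures are 88.5% and 92.8%, and the all-three figures 75.4% and 86.3%: gains of 4.3 and 10.9 points.

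**4. Power with a dose gradient (effects assumed, not in the documents).**

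| Effects A/B/C, mL | A | B | C | All three |
|---|---|---|---|---|
| 100/160/200 | 23.7% → 34.6% | 60.3% → 65.9% | 82.0% → 83.7% | 19.5% → 32.0% |
| 50/150/200 | 6.3% → 11.9% | 54.0% → 58.8% | 82.0% → 83.1% | 5.5% → 11.4% |

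**5. Actual family-wise error.**

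| True configuration | Single-step | Step-down |
|---|---|---|
| All doses null | 0.050 | 0.050 |
| Two null, one very large effect | 0.035 | 0.050 |
| One null, two at 200 mL | 0.019 | 0.040 |
| One null, two very large effects | 0.019 | 0.050 |

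Neither procedure exceeds 0.05 beyond simulation error.

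**6. Agreement with the intervals.** A rejection that only step-down makes has |T| < 2.356. Its single-step interval, estimate ± 2.356 × SE, therefore always includes 0. In the planning case about 15% of trials contain at least one such rejection. In the simulations no single-step rejection was missed by step-down.

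**The case against.** The strongest case for leaving the plan alone has four parts.

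- **The stated target is met.** The only design target is 80% power per test, and the planned method gives 82%. A reader might infer that the trial is underpowered or the adjustment faulty. The documents support neither. They set no target for all three doses, so the 14 points are not a shortfall against the plan. This stands.
- **Single-step buys something.** A reader might infer that it brings no benefit in error control at all. The bound is the same, but the actual error is lower when some doses work and others do not (0.019 against 0.050 in the extreme case). Single-step also gives simultaneous intervals that agree with the tests, and the plan asks for adjusted intervals. Preferring that agreement is legitimate. Both costs stand and must be disclosed; they do not breach the error rate the plan commits to.
- **The planning case is favourable.** It assumes 200 mL at every dose over an eightfold range (100 to 800 µg daily). With a gradient the top dose gains only 1 to 2 points. This also stands.
- **The sponsor's reasons.** A reader might infer that the method was chosen because it beats Bonferroni, so that step-down follows from the sponsor's own reasoning. The documents do not say this. The stated purpose is family-wise error control; the remark on power explains only why a Bonferroni sample size is sufficient.

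What survives is that the decision rule uses the p-value alone, and more power is available for it within the committed error rate.

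**Conclusion.** This is an optional efficiency improvement to a valid plan. Under the plan's own assumptions, step-down testing raises power from 82% to 88% per dose and from 64% to 78% for all three doses, and leaves the chance of at least one success at about 96%. Under an assumed 100/160/200 mL gradient the gains are about 11, 6 and 2 points for the low, middle and top dose. These sizes rest on 99 evaluable per arm, SD 430 mL, correlation 0.5 and the assumed 490 df. They shrink with more evaluable subjects. The price is an actual family-wise error nearer to 0.05 and some rejections that the simultaneous interval does not mirror.

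**What to change.** Before unblinding, apply the simulation adjustment in step-down form to the three Week 8 dose-placebo p-values and base the superiority decision on them.

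- In SAP 8.2, add the step-down option to the adjusted LSMESTIMATE statement, and check on dummy data that the installed software release applies it together with the simulation adjustment.
- In SAP 8.2, 8.2.1.4 and 10.6.1, state that superiority uses step-down adjusted p-values and that the reported intervals remain the single-step simultaneous 95% intervals.
- State in the same places that a dose rejected only by step-down will have an interval that includes 0, and that actual family-wise error can come closer to 0.05 than under single-step while staying within it.
- Record this in SAP 3.8, which now reports no changes, as a change from protocol 12.3.4, where p-values and intervals are adjusted by one method.

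The cost is one code option, short edits to four SAP sections, and footnotes to the primary tables. No additional subjects are needed. Protocol 12.3 allows the SAP to be updated until the blind is broken.

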8.2.1 Statistical/Analytical Issues

8.2.1.1 Handling of Dropouts or Missing Data

The rules to address missing data rules for specific variables are described in Section 7.2 and 8.1.1.

8.2.1.2 Blind Review

A Blind Data Review Meeting is organized just before database lock to finalize the list of protocol deviations which will exclude subjects from the Per Protocol analysis and also to address handling of any outstanding data issues which cannot be resolved prior to database lock. The Data Review Plan will describe the tables, listings and figures used during this meeting, and falls outside the scope of the SAP.

8.2.1.3 Multi-center Studies

No adjustment is done for the multiple centers, and no analysis per center is carried out. The adjustment in the model will be US region.

8.2.1.4 Multiple Comparisons/Multiplicity

Adjustment for multiplicity is applicable only to the primary efficacy analysis. The CIs and the p-values of the comparisons between each dose of CHF 718 pMDI and placebo for the primary efficacy endpoint at Week 8 will be adjusted for multiplicity. The adjustment will be based on the parametric simulation method by Edwards and Berry. At each dose level, the superiority of CHF 718 pMDI will be demonstrated by a **statistically significant** difference (adjusted p-value < 0.05) favoring CHF 718p MDI.

8.2.1.5 Patients Randomized to Incorrect Inhaled Corticosteroid Dose Stratum

If, during randomization, a patient was incorrectly randomized to the wrong stratum for Inhaled Corticosteroid Dose, then the patient will be analysed as if he/she had been assigned to the correct stratum. For example, Subject was stratified to MEDIUM ICS stratum. According to the ICS dosage taken before the study entry the correct stratum was LOW. Subject will be analysed as if he/she had been assigned to the LOW stratum.

9 Interim analyses

Not applicable.

10 Overview of Tables, Listings and Figures

Demographics, asthma and smoking history, spirometry and reversibility will be presented using all three populations (ITT, Safety, PP). Medical history/concomitant diseases and compliance with study treatment will be presented using the ITT and Safety populations. Medications, ACQ score, efficacy variables derived from diary data, compliance use of e-diary, compliance with background medication and protocol deviations will be presented using the ITT population. vital signs, ECG, AEs and laboratory data will be presented using the Safety population.

10.1 Disposition of Subjects

A summary of the number of screened subjects, the number of screening failures and reasons for screening failure will be produced for all enrolled subjects.

A disposition summary of subjects by treatment and overall will include the number (N) of subjects randomized with the number (n) and percentage (%) of subjects who completed or discontinued the study. A subject is considered as completed if the Study Termination Form in the eCRF has “Completed” checked for the question “Specify the subject’s status”. All percentages will be based on the number of subjects randomized.

The reasons for study discontinuation will be also summarized by treatment using absolute counts and percentages, based on the number of subjects randomized. A Kaplan Meier plot will be reported by treatment.

10.2 Protocol Deviations

The number of subjects who had at least one Major Protocol Deviation and all Major Protocol Deviations will be summarized by absolute counts (n) and percentages (%) by treatment for the ITT population. Percentages will be based on the number of subjects in the ITT population. The summary will be repeated for Major and Minor Protocol Deviations.

10.3 Data Sets to be Analyzed

The number of subjects in each population will be summarized by treatment and overall, by absolute counts (n) and percentages (%) for each treatment group. Percentages will be based on the number of randomized subjects. The summary will be repeated by treatment and regions.

10.4 Demographic and Other Baseline Characteristics

10.4.1 Demographic Characteristics

Demographic data, asthma history and smoking habits will be summarized by summary statistics and absolute counts (n) and percentages (%) by treatment and overall for the Safety population, the ITT population and PP population.

10.4.2 Medical History

Medical and Surgical History and Concomitant Diseases will be summarized on a per-subject basis (i.e. if a subject reported the same event repeatedly the event will be counted only once at the specific level of display). Absolute counts (n) and percentages (%) by treatment and overall will be presented for the number of subjects with at least one Medical or Surgical History or Concomitant Disease, and per SOC and per PT within SOC, for the ITT and Safety population. Percentages will be based on the number of subjects in the population.

10.4.3 Screening and Baseline Subject Characteristics

Central spirometry and reversibility test data, Vital signs, ECG results, and Asthma Control Questionnaire at Visit 1 and Visit 2 will be summarized with summary statistics and absolute counts (n) and percentages (%) by treatment and overall for populations as described in Section 6 above.

Reversibility test data will be presented overall and also separately for reversibility calculated during the study and historical reversibility.

Use of rescue medication, asthma symptoms, asthma control days, and PEF during the run-in period will be presented using summary statistics. For these summaries, a minimum of 7 days with some non-missing data during the run-in period are required.

Physical examination results will be only listed.

